8.3 Adverse Events

Any adverse events (as defined by HRA) will be reported to study sponsors and REC.

We will record and consider serious adverse incidents, consistent with organizational policy. These are defined as deaths, life-threatening illness or injury, suicidal or non-suicidal self-injury, serious violent incidents, admissions to hospital or units, any event which results in persistent or significant disability or incapacity, any event for which medical or surgical intervention required to prevent the above and any event otherwise considered medically significant by the Chief Investigator. We will also record adverse events, including but not limited to increased paranoia associated with using the Sleepio application. Additional events will be categorized by study researchers using their clinical judgement.

In case of a serious adverse incident, the responsible clinical team and the ethics committee will be informed. Appropriate actions in response to events will be determined on a case by case basis.

9. FINANCIAL CONSIDERATIONS

There will be no cost associated with Sleepio access for the purpose of this study.

10. DISSEMINATION

The planned project will be written-up to meet the requirements of a Doctorate in Clinical Psychology at the University of Glasgow. Additionally, we plan to disseminate our findings via publication in a peer-reviewed journal. AG and FR will submit a final report at conclusion of the study to the Sponsor(s). Results of the project will also be disseminated within the host service, Esteem. A plain language summary of project results will be disseminated to study participants.

11. PRACTICAL APPLICATIONS

Digital CBT intervention presents a psychological intervention that can be offered under current conditions and is likely to be efficacious. Exploration and treatment of sleep disorders are intended to become part of TAU care in NHS GGC FEP services. A logic model of Sleepio implementation will help inform this.

12. PROJECT TIMETABLE

- August 2020
 - Submission to NHSGGC Research and Development
 - Redrafting as required
- January 2021
 - Ethics submission through IRAS to Research Ethics Committee (REC)
 - Book REC meeting
- February 2021
 - Redrafting as required
 - Approval granted
 - Resubmit to NHSGGC R&D for final approval
- March 2021
 - Begin data collection
- June 2021
 - End data collection
 - Analysis
- July 2021
 - Submission
- August 2021

- Draft paper submission
- September 2021
 - Viva
- Oct 2021
 - Corrections, paper submission

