6.6 Recruitment and Consent

6.6.1. Sample Size

6.6.1.1 Service Users

The Esteem population includes ~250 service users, with ~150 new users per year. Around 80% would be expected to experience clinically significant sleep difficulties (~200/250) and around 50% to experience Insomnia Disorder (~125/250; Reeve et al., 2018a). It is difficult to estimate the rate of eligible persons who will be willing to participate and will be retained in the study. A sample of ~8 for use of the Sleepio intervention has been considered feasible in terms of study resource. Sample size throughout (e.g. recruitment, withdrawal, participation in follow-up) will act as implementation data. As the study is not designed to identify change in symptomatology measures, power calculations have not been carried out. We aim to recruit ~5 service users to participate in optional interviews.

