6.7 Data Collection

6.7.1 Implementation Data

We will gather data on eligibility, consent rates and the rate of service user participants beginning intervention. We will gather data on clinical sleep disorder assessment outcomes. Sleepio intervention will span week 0 to week 10. Usage data will be collated throughout these 10 weeks via the application. This data will comprise the rate of completion of the six sessions contained in the intervention and of sleep diaries. These metrics will allow us to ascertain intervention adherence, attrition and completion. We will further record rates of attendance to complete symptomatology measures. In analysis, these data will be represented by rates and summary statistics.

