6.7.2 Measures

Symptomatology measures will be completed with service user participants using NHS Attend Anywhere or at in-person appointments at baseline (week -1), and at week 11. Researchers completing these appointments are NHS GGC employees with pre-existing access to Attend Anywhere. We will complete symptomatology measures using Online Surveys (<https://www.onlinesurveys.ac.uk/>; formally **Bristol Online Surveys**). Online Surveys is UK based, Data Protection Act 2018-compliant and has ISO certification. If sessions are undertaken in person, these measures will be completed on paper. The study researchers are not aware of any issues in relation to the suitability, ease of use or acceptability of these measures in this service user group. The baseline appointment will also allow participants to set up the Sleepio application and complete its initial assessment.

Service user participants will be assessed with measures of:

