6.7.3 Qualitative Interviews

6.7.3.1 Service Users

Service users will be provided with the *option* to participate in semi-structured interviews prior to beginning intervention and/or after completing the intervention. Each interview appointment will last ~45 - 60 minutes. Pre-intervention interviews will be undertaken prior to the baseline symptomatology measures appointment, at approximately week -2. They will focus on service users' expectations for the Sleepio intervention (see Interview Schedule).

Post-intervention interviews will be undertaken after completing follow-up symptomatology measures, at approximately week 12. They will focus on service users' experiences of the Sleepio intervention (see Interview Schedule). Post-intervention, participants will be purposively sampled to include a range of service users reflecting their engagement with the Sleepio App.

Interviews will be undertaken using a NHS Microsoft Teams meeting from an NHS GGC computer or in-person at an Esteem base. Attend Anywhere cannot be used as it is not possible to record on this platform. As with Attend Anywhere, researchers have pre-existing access to this as NHS GGC employees and it is considered secure for NHS use. Interviews will be digitally video recorded and auto-transcribed for purposes of analysis. These are inbuilt features of Microsoft Teams meetings. If interviews take place in person, data will be collected in the form of audio recordings on an encrypted recording device and transcribed by researcher FR.

Service users can participate in pre- or post-intervention interviews, or neither.

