6.9.1. Quantitative

Descriptive quantitative information will be provided for implementation measures (percentages, rates, mean, median, variance, 95% confidence intervals). This will include reporting data on attrition rates and loss to follow-up.

Descriptive quantitative information will be provided for sleep assessment.

Analyses of symptomatology measurements will not be focused on statistical significance but will be quantitatively detailed (estimated 95% confidence intervals, variance) to assess the likely range of treatment effects. Our study is not designed nor powered to detect statistical differences in measures over time. Exploratory analysis of the relationship between symptomatology variables will be undertaken.

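### Does the March to June 2021 timetable leave too little time for about eight service users to reach week 11, so that a calendar cut-off is counted as attrition?

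*Protocol*

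**What the plan says.** Section 12 (Project Timetable) is a month-by-month list. Data collection begins in March 2021; June 2021 carries both "End data collection" and the analysis; submission is in July.

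The schedule for each service user is in sections 6.7.1 to 6.7.3:
- Symptom measures are taken "at baseline (week -1), and at week 11".
- "Sleepio intervention will span week 0 to week 10".
- Interviews are optional: "Service users can participate in pre- or post-intervention interviews, or neither". The early one falls at about week -2. For the late one: "Post-intervention interviews will be undertaken after completing follow-up symptomatology measures, at approximately week 12".
- Section 6.7.3.2 holds the keyworkers' late interviews, also optional, until every service user has finished the intervention.

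Three sections treat participation as a result in its own right. Section 6.6.1.1: "Sample size throughout (e.g. recruitment, withdrawal, participation in follow-up) will act as implementation data". Section 6.7.1: "We will further record rates of attendance to complete symptomatology measures". Section 6.9.1, on the implementation measures: "This will include reporting data on attrition rates and loss to follow-up".

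Section 6.6.1.1 sets the sample at about 8 and makes no power calculation. The protocol gives no recruitment period, no last-baseline date and no rule for someone whose week 11 would fall after collection ends.

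**The concern.** A 12-week follow-up inside a window of about four months leaves only the first few weeks for enrolment. Someone who enters later cannot be seen at week 11 before the end of June. If that person were then counted with those who dropped out, a limit set by the calendar would appear in the results as poor retention. A low recruitment count could likewise be read as low reach when the entry period was simply short.

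In most studies this would be a practical matter. Here recruitment, attendance, attrition and loss to follow-up feed the logic model, and with about eight people each one carries a lot of weight.

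**Working it through.** **Inputs.** Start: March 2021, no day (section 12). I try 1 March, 12 March (the version date in the synopsis, used only as a plausible start) and 31 March. Close: June 2021, no day (section 12). I try 1, 15 and 30 June. Span from baseline to last measures: week -1 to week 11, which is 12 weeks or 84 days (section 6.7.2). Sample: about 8 (section 6.6.1.1). The protocol states no recruitment window, so there is no figure of its own to reproduce.

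**Last baseline for a 30 June close** (30 June minus the span):
- To reach the week-11 measures: 30 June - 84 days = 7 April.
- To complete usage to week 10 only (week -1 to week 10, 77 days): 30 June - 77 days = 14 April.
- To fit the optional week-12 interview (91 days): 30 June - 91 days = 31 March.
- To fit both optional interviews (week -2 to week 12, 98 days): the week -2 contact by 24 March, so again a baseline by 31 March.

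**Weeks available for baselines that reach week 11** = (close - start)/7 - 12:

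| Close | Last baseline | From 1 March | From 12 March | From 31 March |
|---|---|---|---|---|
| 30 June | 7 April | 121/7 - 12 = 5.29 | 110/7 - 12 = 3.71 | 91/7 - 12 = 1.00 |
| 15 June | 23 March | 3.14 | 1.57 | none |
| 1 June | 9 March | 1.14 | none (0.43 short) | none |

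**Pace needed for eight baselines, 30 June close:** 8/5.29 = 1.51 per week from 1 March; 8/3.71 = 2.15 per week from 12 March. Section 6.6.1.1 expects about 125 of about 250 service users to have Insomnia Disorder, so eight is 8/125 = 6.4% of that pool.

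**Effect of one misclassified person:** 1/8 = 12.5 percentage points. Observed loss goes from 0/8 (exact 95% interval 0 to 36.9%) to 1/8 (0.3 to 52.7%).

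**Keyworker interviews:** a baseline on 7 April gives week 0 on 14 April and week 10 on 23 June, leaving 7 days to 30 June. This is the extreme case, in which the last user enters on the last possible day.

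**The case for a change.** The strongest case for acting is that 3.7 to 5.3 weeks is a generous reading. A close before 30 June or a start late in March shortens it, and some combinations leave no time at all. Version 5 is dated 12 March, and section 7.1.2 still describes approvals as to be obtained before recruiting, so a start on 1 March is doubtful. Referral, information, consent, return of signed forms and screening all come before baseline, and one researcher does most of this work. Section 6.8 covers withdrawal, stopping Sleepio while staying in the study, and termination by the sponsor, but not a participant overtaken by the planned close. A last-baseline date is a timetable item that belongs in a protocol and would cost almost nothing.

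Much of this stands: the subtraction is right, the window is tight and the date is absent. It still does not show an error.
- The combinations that leave no time require days that the protocol does not set. Month-level entries are compatible with a workable schedule.
- The harm needs three things together: a baseline after the cut-off, a rigid close, and the team recording as lost someone whose appointment never fell due. The protocol states none of these.
- The 7 April date does not apply to usage. A baseline up to 14 April still completes week 10 by 30 June, and usage is collated through the application without a visit.
- The 12.5-point step belongs to any rate with a denominator of eight. The two exact intervals overlap almost entirely, so a descriptive reading would hardly change.
- Ineligibility and consent proportions are not distorted by a late close, and a missed optional interview is not loss to follow-up.

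**Conclusion.** No change to the plan is needed. With a 30 June close, baselines must be complete by 7 April for everyone to reach week 11. That gives 5.3 weeks from 1 March or 3.7 weeks from 12 March, and less with a later start or earlier close. These figures rest on assumed days, since section 12 gives only months. On those assumptions the schedule is tight but feasible for about eight people.

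Nothing in the protocol contradicts itself here, and following it as written produces no wrong result. The unwritten parts are a last entry date and the ordinary convention that contacts not yet due at close are reported apart from attrition and loss to follow-up. The protocol commits to no opposite rule. The team that runs the appointments will know who was cut off by the calendar, and a reporting convention of this kind is commonly left to an analysis plan. Stating the date would be a courtesy to readers; the study's conclusions do not depend on it.
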